## **5.4. Restrictions**

### **Dietary and Fluid Restrictions**

#### *Caffeine*

Xanthine containing products (e.g., caffeine in coffee, tea, chocolate, energy drinks) will not be allowed from 10 hours before outpatient visit and admission to the clinical centre, and for the time of outpatient visit.

#### *Alcohol*

Consumption of alcohol and alcohol-containing foods, medications or beverages must be avoided from 48 hours before admitted to the clinical centre, during whole Treatment Phase until discharge from the clinical centre after completed Treatment Phase. Subjects during the Follow-Up period, are to be required not to consume beverages containing alcohol up to first follow-up visit. Later it is recommended to not consume more than 3 units (males) or 2 units (females) per day (1 unit is equal to approximately ½ pint [284 mL] of beer, one small glass [125 mL] of wine, or one measure [25 mL] of spirits).

#### *Meals during stay at the clinical centre*

During in-house stay (Day 85) at the clinical centre only meals and fluid served at clinical centre will be allowed.

#### *Fasting*

Dosing on ambulatory visits in the morning will be preceded by an overnight fast of at least (6) hours. Water intake will be allowed up to 1 hour before dosing and from 1 hour after dosing (excluding amount of water allowed for IMP administration). Patients should be fasted 2 hours after IMP administration in the morning and in the evening. In the evening IMP should be administered on fasting condition at least 2 hours after a previous meal.

MTX can be administered together with the Investigational Product however patient should continue the scheme of MTX administration from before the study.

### **Lifestyle Considerations**

#### *Drugs of abuse*

Subjects must refrain from use of recreational drugs for the duration of the study.

*Nicotine*

Cigarette smokers will be allowed to smoke however it is necessary to refrain from smoking 90 minutes before an ambulatory visit.

*Strenuous activity*

Subjects should refrain from carrying out heavy physical training (e.g., long distance running, weight-lifting, or any physical activity to which the subject is not accustomed) from 48 hours prior to admission to the clinical centre, until the final Follow-up Visit. Subjects should neither start any new physical training nor increase the intensity of their usual training during study participation. Subjects may participate in light recreational activities during study, including rehabilitation allowed by the Investigator.

### **5.5. Prior and Concomitant Treatments**

Any medicinal product prescribed or over-the-counter (OTC), taken by a subject other than the IMP, is considered concomitant medication.

The following concomitant medications may be continued during the study as background RA treatments. The dosage of the basic therapy is not to change for the entire trial from the screening through the end of the study and should be stable within indicated period of time before the randomization process and within dosing with the investigational product.

1. **Methotrexate (MTX)** (required background RA treatment). Subjects will continue on their pre-study dose of MTX (supplemented with folic/folinic acid). Subjects must have been taking oral or parenteral methotrexate for at least 3 months (prior to screening) at an adequate dose to determine that the subject had an inadequate response to MTX. Inadequacy is to be defined by the Investigator's and subject's opinions that the subject did not experience eligible benefits from methotrexate plus the presence of sufficient residual disease activity to meet the inclusion criteria. The MTX dose and route of administration must have been stable for at least 8 weeks before first dose of study drug, and the dose and the route of administration must remain stable during the whole study period. Allowed methotrexate doses are 15 to 25 mg, inclusive, weekly, unless there is documented (epicrisis, the source documentation) intolerance or toxicity from these doses, in which case a dose  $\geq 10$  mg, inclusive, may be used.
2. Nonsteroidal Anti-inflammatory Drugs (NSAIDs), including selective Cyclooxygenase-2 inhibitors ("COX-2 inhibitors"), administered according to local guidelines at stable doses 4 weeks before Day 1/ baseline.

3. **Opioids** (Tramadol) at a stable dose beginning at least 4 weeks prior to first study dose. Opioids other than tramadol are not allowed during the study and should be ceased at least 4 weeks before Day 1/Baseline.
4. **Paracetamol** at doses 1500 mg (500 mg three times a day) or according to other treatment plans fixed individually. In case of exacerbation of the disease ad hoc administration of paracetamol is permitted. Subjects should refrain from paracetamol 24h before an ambulatory visit.
5. Low dose oral **corticosteroids** at a stable dose  $\leq$ 10 mg per day beginning at least 4 weeks prior to first IMP dose up to the end of the study. Intravenous, intramuscular and intraarticular administration of corticosteroids is forbidden 6 weeks before Day1/ baseline up to the end of the study. Topical and inhalation corticosteroids are allowed before and during the present clinical trial.

#### **5.6. Prohibited medications:**

1. Current therapy with any disease-modifying antirheumatic drug (DMARD) other than MTX. All DMARDs (except for MTX) must be ceased before Day 1/ baseline, as follows:
  - **1 month before:** etanercept, sulfasalazyna, chlorochina/hydroksychlorochina;
  - **3 months before:** leflunomide (**4 weeks** in case of cholestyramine washout);
  - **3 months before:** adalimumab, golimumab, infliximab, certolizumab, tocilizumab, gold, cyclosporine, penicillamine, azathioprine

**NOTE:** For biological agent, previous use of one (and only one) treatment listed above (tocilizumab or TNF-alpha inhibitor) is allowed, if administered for less than 3 months or ceased because of other than lack of effectiveness causes.

2. Previous use of (at any time)
  - Cyclophosphamide
  - Tacrolimus
3. Previous use of JAK inhibitors;
4. Previous use of biologic agent other than tocilizumab or TNF-alpha inhibitor except for biologic agents that were considered as DMARDs and used as an investigational medicinal product within a clinical trial if a 30 days or 5 half-lives (whichever is longer) washout period was applied.

**NOTE:** Subjects cannot take part collaterally in different clinical trials and administer other IMPs at the same time.

## 5.7. Rescue medications

Any exacerbation of the disease that requires the implementation of additional rescue therapy requires consultation with the study Sponsor. Each situation will be considered individually.

## 5.8. Contraception Rules

In order to prevent from pregnancy during the presence clinical trial a woman must be either:

- c. Not of childbearing potential:
  - postmenopausal (>45 years of age with amenorrhea for at least 12 months, without using exogenous hormonal contraception and with FSH  $\geq 40$  IU/L),
  - permanently sterile (hysterectomy, bilateral salpingectomy; bilateral oophorectomy); or otherwise be incapable of pregnancy.
- d. Of childbearing potential and using a double contraception including a barrier method (condom or occlusive cap) and a highly effective method of birth control (listed below).

**NOTE:** highly effective methods of contraception are defined as:

- established use (i.e. at least 8 weeks prior to Day 1) of combined (estrogen and progesterone) hormonal contraception associated with inhibition of ovulation (oral, intravaginal, transdermal, injectable) or progesterone-only hormone contraception associated with inhibition of ovulation (oral, injectable);
- intrauterine device (IUD) or intrauterine hormone-releasing system (IUS);
- bilateral tubal occlusion/ligation
- vasectomized partner (vasectomized partner should be the sole partner for that subject and the absence of sperm should be confirmed).

**NOTE:** sexual abstinence, defined as refraining from heterosexual intercourse throughout the study and for 12 weeks after the last IMP dose, is acceptable as a sole contraception method when this is in line with the preferred and usual lifestyle of the subject.

- e. Participant (a man) who is sexually active with a woman of childbearing potential must agree to use a double contraception including a barrier method (male condom) and a highly effective method of contraception (highly effective method of contraception are listed above) during the study and 12 weeks after the last dose of CPL409116/ placebo administration.

**NOTE:** Male subjects are responsible for informing his partner(s) of the risk of becoming pregnant and for reporting any pregnancy to the study doctor.

**NOTE:** Participants (males and females) are furthermore willing to use contraception methods for 12 weeks after the last dose of CPL409116/ placebo administration. It is crucial to maintain appropriate methods of contraception if it is planned to continue methotrexate administration after the end of the study.

[figure not shown]
## 6. INVESTIGATIONAL MEDICINAL PRODUCT

### 6.1. Physicochemical properties of CPL409116

Active substance: CPL409116

Chemical name: (R)-7-((3,3-Dimethylpiperidin-4-yl)amino)-2-(6-methoxypyridin-2-yl)pyrazolo[1,5-a]pyrimidine-6-carboxamide

Chemical structure:

Molecular formula: C25H26N10O2

Molecular weight 498.55 g/mol

### 6.2. Identity of the Investigational Medicinal Products

PG24 is to contain CPL409116 (Table 2). It is to be administered in immediate release tablets. Tablet is to be suitable for oral administration. PG24 is to be in tablets containing 60 mg of API (PG242).

Placebo product PG24P also is to be prepared in tablets to correspond to the investigational product (60 mg CPL409116 (PG24P2). Tablet is to be suitable for oral administration.

Table 2. The composition of PG24 and placebo PG24P2.

Tablet Type	Active Substance (mg)	Excipients (mg)
PG24	60	40
PG24P2	0	40

### **6.3. Supply, Packaging, Labeling and Storage**

CPL409116 compound in formulation (PG24) is to be in tablets containing 60 mg (PG242) of active substance. For the study phase II the PG242 and PG24P2 tablets are to be prepared in the same way in the immediate release formulation. The placebo appearance will be exactly the same as the drug, so that neither the subject nor the Investigators not know what is to be administered.

Tablets are to be packed on three levels. The first is a single aluminum blister in which one tablet is to be closed, consider as a primary package. The aluminum blisters are to provide the tablets with effective protection against moisture and light, what is required for the IMP to retain its properties. Tablets in blisters are to be packed in an outer package- envelopes and cardboard boxes.

Label templates are to be provided in a separate document.

Test item product should be stored at temperature below 25°C.

### **6.4. Subject Identification and Randomization**

#### **Screening Numbers**

At Screening, patients will be assigned a unique subject identification number (or subject identifier). Enrolled patients who drop out of the clinical study before randomization will retain their subject identification number.

#### **Randomization Codes**

At the end of the Screening, patients will be assigned a randomisation code generated by a randomisation system in the electronic case report form. The randomisation code will consist of four letters. The random coding system is described in a separate document.

Once a randomization code has been allocated to one subject, it may not be assigned to another subject.

## **6.5. Administration of Investigational Medicinal Products**

Starting from Day 1, the IMP will be administered after a minimum 6 hours overnight fast with approximately 250 mL water in the morning. After IMP administration in the morning and in the evening subjects should stay fasted for 2 hours. Patients should be 2 hours fasted before IMP administration in the evening. Subjects must remain in an upright position for at least 1 hour after dosing. MTX can be dosed together with IMP however it is recommended to apply MTX according to a previously fixed treatment plan.

## **6.6. Dosing**

All tablets are to be administered orally. CPL409116 tablets should be taken under fasted conditions (after a minimum 6 hours overnight fast in the morning minimally, 2 hours after the last food consumption in the evening and 2 hours prior to the next meal consumption in the evening), but preferably should be taken consistently in the same manner and at the same time each day. Exceptionally on study visit days patients will be instructed to refrain from dosing at home, and will take the study medication at the clinic. Subjects should swallow the tablets with water to a total volume of approximately 250 mL. It is important that subjects swallow the investigational product whole, and that they not manipulate or chew the investigational product prior to swallowing. Sites will instruct subjects on the proper way to remove tablets from blister packs and how subjects will administer the IMP at home. Subjects will be instructed to self-administer their study medication according to administration instructions provided to the subject. Subjects will be instructed not to remove tablets from the blister packaging until the time of dosing. Patients will be given a subject diary and provided with instructions on the completion of the diary. The diary won't be filled during Patient's visit at Site. The data during ambulatory visits will be recorded in source documentation.

In this phase of the proof of concept clinical trial patients are to take tablets containing 60 mg of IMP (Table 3).

Table 3. The number of tablets for each potential dose of CPL 409116 for the study.

PG24 DOSE	NUMBER OF TABLETS (60 mg)
60 mg	1
120 mg	2
240 mg	4

Patients are to be randomized to one of four study arms with assigned appropriate dose of CPL409116: 60 mg (study arm 1); 120mg (study arm 2) or 240 mg (study arm 3) administered twice a day and with assigned placebo (study arm 4). Every patient included in the study and randomized is to take the same number of

tablets (4 tablets) in the morning and in the evening to blind substances which are to be taken by participants. This number of tablets (4 tablets per administration) is to be corresponding to the highest possible dose of CPL409116 equals 240 mg per administration (4 tablets). The table below shows the number of tablets which are to be taken by participants in particular arms of the study.

Table 4. The number of tablets administered by patients depending on the study arm.

	Study arm	CPL116 (60 mg) 60 mg per administration	CPL116 (60 mg) 120 mg per administration	CPL116 (60 mg) 240 mg per administration	PLACEBO per administration	Total
Number of tablets	1	1	-	-	3	4
	2	-	2	-	2	4
	3	-	-	4	-	4
	4	-	-	-	4	4

In the clinical unit blisters with appropriate tablets are to be opened by pharmacist or delegated person and prepared for administration in order to eliminate risk of mistake. Patients are to take appropriate number of tablets with active substance or placebo.

## 6.7. Compliance and IMP Accountability

Dosing will be performed by trained and qualified personnel designated by the Investigator during the ambulatory visits in the morning. The date and time of IMP dosing will be documented on each dosing day during the outpatient visits. During home dosing periods (including evening dosage), time of IMP and methotrexate dosing should be documented in the patient's Diary. Comments will be recorded if there are any deviations from the planned dosing procedures. A single dose is to be consider as a compliant when all 4 tablets are administered, and administration is without any emesis occurring within 2 hours after IMP administration. A patient is to be considered as a complier with dosing regimen when at least 80 % of the doses are compliant (at least 136 doses). Compliance from days of home dosing will be verified by a designated person taking into account data from the Patient's diary and empty blisters patient brings on the next visit and during phone call visits. On Day 85 subjects will be hospitalized up to Day 86 in the morning due to donation of blood samples for PK analysis in 13 timepoints. Subjects can spend Day 85 night to Day 86 outside of the clinic but it is necessary to return on Day 86 in the morning in order to donate the last sample of blood 24h after morning CPL409116 administration on Day 85. The Sponsor shall supply an adequate quantity of the investigational medicinal product (IMP) and the placebo, both for administration and as a backup, along with the respective certificates of analysis (CoA). The amount of each product should be sufficient to account for any loss resulting from its potential damage or subject's withdrawal.

The unblinded pharmacist or delegated person is obliged to store the products in a safe place, with limited access to third parties. The products are to be securely stored under pre-specified conditions, in accordance with applicable regulatory requirements. The products will remain under the supervision of the pharmacist or delegated person and released solely for the administration purposes and IMP dispensing for home dosing, according to the study protocol. On outpatient visits during the treatment phase, patient is to return used blisters and product that was not administered on proper day, and the accountability of the IMP dispensed previously for home dosing will be checked and documented by a designated person. The study designated pharmacist or delegated person is to be responsible for the investigational product in the clinical center during the entire study period. At the end of the study, the number of unused IMP will be determined, and the product will be returned to the Sponsor. Adequate records documenting receipt, use or other disposition of the investigational product will be kept by the designated person. The unblinded study monitor will verify these documents throughout the course of the study.

#### **6.8. Blinding and Breaking the Blind**

The clinical study will be performed in a double-blind manner, so the identity of investigational drug and placebo will not be known to investigators, research staff and subjects. At the clinical centers, there is to be an unblinded pharmacist and another unblinded person responsible for the IMP management in accordance with proper pharmaceutical manual. Unblinded staff members are not to be involved in any patient evaluation and examination.

The study blind may be broken only in a medical emergency (where knowledge of the study drug administered would affect the treatment of the emergency). The decision to break the blind will be made on a case-by-case basis, at the discretion of the Investigator, and if possible, in collaboration with the Sponsor and/or Medical Monitor or responsible designee. If the blind is broken, the CRO and Sponsor must be informed as soon as possible. The date, time and reason for unblinding will be documented in the CRF and in the source data. The applicable standard operating procedure (SOP) will be followed for blind breaking procedures.

After database lock, the overall randomization code will be broken only for reporting purposes.

Suspected unexpected serious adverse reactions (SUSARs), that are subject to expedited reporting, should be unblinded by the Sponsor before submission to the regulatory authority and the Institutional Review Board (IRB) or Independent Ethics Committee (IEC). Information about SUSAR will also be sent to all Investigators (after the patient has been unblinded).

### **6.9. Treatment of Overdose**

In the event of overdose (defined as any dose above that specified in the protocol), the Investigator should contact the CRO and the Sponsor immediately and closely monitor the patient for AEs/SAEs. Supportive symptomatic treatment can be provided for overdose-related AEs. Information regarding the quantity of the excess dose, as well as the duration of the overdosing, should be documented.

Patients should be instructed NOT to take a substitute dose if vomiting occurs after self-dosing at home. Missed doses should be skipped and NOT taken as a double dose at the next dosing timepoint. Missed dose should be recorded.

Symptomatic support measures should be used in the case of excessive pharmacological effects or overdose.

The Investigator should follow-up and document the course and the outcome of each overdose even if the subject was withdrawn from the clinical study or if the clinical study has finished and if the patient agrees. Any SAE that occurs due to overdose must be recorded on the Serious Adverse Event Report Form and must be reported by Investigator to the Sponsor within 24 hours of becoming aware of the event.

## **7. DISCONTINUATION**

### **7.1. Study Stopping Rules**

The stopping rules described in this section of the clinical study protocol (CSP) are applicable to stopping the study. IMP, CPL409116, dosing may be halted temporarily to investigate before the entire study is terminated.

Measures to ensure data integrity and safety of research subjects will be detailed in the Safety Management Plan (SMP) and the Data Management Plan (DMP).

If the Investigator, the Medical Monitor, responsible designee, or the Sponsor becomes aware of conditions or events that suggest a possible hazard to subjects if the clinical study continues, then the clinical study may be terminated after appropriate consultation among the involved parties. The clinical study may be terminated at the Sponsor's discretion also in the absence of such a finding.

Should the study be terminated, and/or the study center closed for whatever reason, all documentation pertaining to the study and study drug must be returned to the Sponsor. Any actions of the CRO required for assessing or maintaining subject safety will continue as required, despite termination of the study by the Sponsor.

## 7.2. Safety Criteria

After the first dose of IMP, a subject may discontinue from the study for a variety of reasons. Treatment discontinuations may be initiated by a subject or may become medically necessary due to AEs, required treatment with a disallowed medication or therapy, or other reasons, as determined by the Investigator. If a subject discontinues treatment, their participation in the trial will be discontinued. Discontinued subjects should be encouraged to complete all early termination and Follow-up assessments with early termination assessments conducted as soon as possible after the subject is withdrawn.

An individual subject will be withdrawn from the study if:

- the subject withdraws his/her consent, which he is allowed to do at any time and without the need to justify his/her decision;
- the subject requires treatment with any medication known or suspected to interfere with the study medication;
- the subject is no longer able to participate for other medical reasons (e.g. surgery, adverse event);
- the subject – in spite of the earlier evaluation upon recruitment – is suspected or found not to comply with eligibility criteria;
- there is evidence or sound suspicion that the subject fails to comply with the protocol directives (compliance with the treatment schedule, non-adherence to dietary rules or other study restrictions that may have an influence on study results, non-attendance at study assessments);
- any other condition occurs which in the opinion of the Investigator no longer justifies or permits a safe participation of the subject.

Each patient has the right to withdraw from the study at any time without prejudice. The Investigator may discontinue any patient's participation when he/she feels it is necessary, for any reason including adverse events or Clinical Study Protocol violation. The patient should always be informed about the reason for his discontinuation. Reasons for the withdrawal of an individual patient from the study will be recorded by the Investigator in the Case Report Form and in the Clinical Study Report. In the case of withdrawal caused by an adverse drug reaction, the patient will be under observation until symptoms of the reaction have subsided.

In the case of emesis, an individual patient is to be withdrawn from the study if:

- the subject suffers from moderate or severe emesis within 4 hours in two consecutive IMP administrations. If emesis occurs within 4 hours post-dose and is mild or moderate or emesis occurs

after 4 hours post-dose, discontinuation of the subject depends on the Investigator's judgment and decision.

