## 1. PROTOCOL SUMMARY

### 1.1. Protocol Synopsis

Protocol Title	A 12-week, phase II, multicentre, randomised, double blind, efficacy and safety study comparing CPL409116 to placebo, in combination with methotrexate in participants with active rheumatoid arthritis who have an inadequate response to methotrexate.
Study Numbers	Sponsor Protocol No.: 03JAK2021
Development Phase	Phase II
Sponsor	Celon Pharma SA
Study Center	This study will be conducted at multiple clinical centers
Study Objectives	
Primary Objective:
 
Efficacy:
 

- to determine the efficacy of CPL409116 at 12 weeks, in subjects with active RA who have had an inadequate response to methotrexate (MTX).

 
Secondary Objectives:
 
Efficacy:
 

- to determine the effect of CPL409116 at 3 different doses, compared to placebo in subjects with rheumatoid arthritis;

- to assess dose-response and exposure- response relationship for CPL409116.

 
Safety:
 

- to evaluate safety and tolerability of CPL409116 administered at doses: 60 mg, 120 mg or 240 mg twice a day for 12 weeks in subjects with RA.

 
Pharmacokinetics:
 

- to evaluate pharmacokinetic (PK) parameters for CPL409116 and metabolite M3 in patients with RA.

 

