#### **Intensity**

The Investigator will assess all AEs for severity in accordance with the following standard ratings:

1. Mild: Ordinarily transient symptoms, does not influence the performance of the subject's daily activities. Treatment is not ordinarily indicated;
2. Moderate: Marked symptoms, sufficient to make the subject uncomfortable. Moderate influence on the performance of the subject's daily activities. Treatment may be necessary;
3. Severe: Symptoms cause considerable discomfort. Substantial influence on the subject's daily activities. May be unable to continue in the study and treatment may be necessary.

When changes in the intensity of an AE occur more frequently than once a day, the maximum intensity for the event should be noted for that day. Any change in the severity of signs and symptoms over a number of days will be captured by recording a new AE, with the amended severity grade, and the date (and time, if known) of the change.

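### Protocol 7.2 gives two conflicting instructions for moderate emesis within 4 hours of two consecutive doses: mandatory withdrawal in one sentence, Investigator discretion in the next

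*Protocol*

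**What the plan says.** The emesis rule closes Protocol section 7.2 (Safety Criteria). It opens in mandatory terms, "In the case of emesis, an individual patient is to be withdrawn from the study if", and states one condition: "the subject suffers from moderate or severe emesis within 4 hours in two consecutive IMP administrations".

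The sentence that follows reads "If emesis occurs within 4 hours post-dose and is mild or moderate or emesis occurs" and continues "after 4 hours post-dose, discontinuation of the subject depends on the Investigator's judgment and decision".

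Three other statements bear on the rule:

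- Earlier in 7.2, stopping treatment is tied to leaving the trial: "If a subject discontinues treatment, their participation in the trial will be discontinued".
- Section 7.2 also gives a general power: "The Investigator may discontinue any patient's participation when he/she feels it is necessary".
- Protocol section 8.1, under Intensity, defines the grade that appears in both emesis sentences: "Moderate: Marked symptoms, sufficient to make the subject uncomfortable".

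The SAP neither restates nor clarifies the emesis rule.

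**The concern.** The grade *moderate* stands in both sentences with the same 4-hour window. The first sentence requires withdrawal; the second leaves the decision open. The second sentence sorts cases by grade and timing only. It contains no wording that confines it to single episodes or to cases the first sentence has not already caught.

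The synopsis states "This study will be conducted at multiple clinical centers", so different investigators will read this text. Because stopping treatment ends participation, the reading chosen can decide whether a patient stays in the trial. Three things in the analysis depend on that:

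- **Withdrawals due to adverse events.** Their incidence is part of the secondary safety endpoint (Protocol synopsis, Criteria for Evaluation; SAP, Secondary endpoints).
- **Per-protocol membership.** The PP set requires completion of the treatment period to Day 85 (Protocol 10.2; SAP 3.1), and SAP 3.3, Table 2, excludes patients with no valid DAS28-CRP at Day 85.
- **The scheduled Day 85 DAS28-CRP.** This is the primary endpoint assessment, and a patient withdrawn before Day 85 will not have it on schedule.

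**Working it through.** No formula in the plan rests on this rule and there is no stated figure to reproduce. The check is to take every combination of grade, timing and repetition and read off which emesis sentence of section 7.2 applies. Grades are those of section 8.1 (mild, moderate, severe). Timing and repetition are the categories used by the two sentences themselves.

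| Grade | Within 4 h, two consecutive doses | Within 4 h, not two consecutive doses | After 4 h |
|---|---|---|---|
| Mild | Discretion | Discretion | Discretion |
| Moderate | **Mandatory and discretion** | Discretion | Discretion |
| Severe | Mandatory | **Neither sentence** | Discretion |

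Of the nine cells, seven have exactly one instruction. One has two that conflict (moderate, within 4 hours, two consecutive doses). One has none (severe, within 4 hours, not recurring at the next dose).

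Could something else in the documents settle the conflicting cell?

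1. *The definition of the grade.* Section 8.1 gives one definition of moderate, so the two uses cannot be told apart by severity.
2. *The general power in section 7.2.* It lets the Investigator discontinue a patient. It does not let the Investigator keep a patient whom another sentence says must be withdrawn, so it does not decide between the two.
3. *The emesis window in Protocol 6.7.* The 2-hour window there defines a compliant dose. It serves another purpose and does not bear on withdrawal.
4. *The SAP.* It is silent on the rule.

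The empty cell is less serious. The list in 7.2 provides for withdrawal when, in the Investigator's opinion, safe participation is no longer possible, and the general power quoted above applies as well.

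Scale, as an illustration only, using the planned numbers in the synopsis and Protocol 11.2:

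- One patient in an arm of 25: 1/25 = 4 percentage points of that arm's rate of withdrawal due to adverse events.
- Planned dropout allowance per arm: 25 − 21 = 4 patients, and 4/25 = 16%, which matches the stated 16%.
- If 1 to 3 patients per arm met the conflicting condition (an assumption; the documents give no emesis rate), that is 1/25 to 3/25, or 4% to 12% of the arm. This is the widest gap between readings, with all withdrawn under one and all kept under the other. Since 3 is below 4, such losses could sit inside the allowance.

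**The case against.** The strongest reply is that the two sentences can be read together without conflict. The first is the specific rule, for emesis that recurs at the next dose; the second covers whatever falls short of that. If the second sentence overrode the first, the word *moderate* in the mandatory rule would do no work. This reading is plausible and may be what was meant. The text does not state it, however, and a withdrawal rule should not depend on each site reaching the same inference. The empty cell does not count against this reading, because the second sentence lists only mild or moderate emesis within 4 hours. Severe non-recurring emesis is outside both sentences whichever reading is taken.

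The reply is also right that the consequences are limited. Withdrawn patients have an early-withdrawal visit with DAS28-CRP and ACR assessments, ECG, laboratory tests and adverse event monitoring (Protocol 9.4), and two safety follow-up visits (Protocol 4.6). Adverse-event discontinuation is already largely at the Investigator's discretion under 7.2, so some variation between sites exists whatever the emesis rule says. Only one narrow cell is in conflict.

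A reader might infer more than the documents support:

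- **That sites will in fact diverge.** The wording permits it; nothing shows that it will happen.
- **That the rule decides whether the patient's efficacy and safety data exist at all.** It does not, given the early-withdrawal assessment and follow-up. Week 8 data are also already in hand if the emesis occurs after Day 57.
- **That affected patients are a loss from the 21 evaluable per arm.** They come from the 25 randomised, and the 21 is already net of planned dropout.
- **That the loss would fall on the active arms.** That would require dose-related emesis, for which the visible text gives no human data.

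**Conclusion.** Section 7.2 is wrong as written: it contradicts itself for moderate emesis within 4 hours of two consecutive doses. This is an internal contradiction, not a design choice. It also leaves severe, non-recurring emesis within 4 hours without an emesis-specific rule, with the general provisions of 7.2 as the only cover.

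The same patient can therefore be withdrawn at one site and kept at another. The size of any effect is unknown because no emesis rate is given. Beyond the 4 points per affected patient shown above, nothing can be quantified without assumption, and no effect on power or on the Week 12 comparison is established.

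Severity is minor. The point is worth correcting because the rule bears on a named safety endpoint and on per-protocol membership. The conclusion rests only on the wording of the two adjacent sentences and on the absence of any statement of precedence.

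**What to change.** Reconcile the two emesis sentences in Protocol 7.2 so that each combination of grade (mild, moderate, severe), timing (within or after 4 hours) and number of consecutive doses falls under exactly one rule, including severe emesis within 4 hours that does not recur. Send the reconciled text to all sites. Which rule applies in each case is for the sponsor's medical team to decide; no view is taken here.

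The cost is one clarified passage in the protocol and a site memo. Assessments, patient numbers and the SAP are unaffected.
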